3.8.9.5 Reporting Serious Adverse Events and Pregnancy

An AE that meets any of the serious criteria must be reported to Covance within 24 hours from the time that site personnel first learn of the event, using the SAE Report form provided for the study. All SAEs must be recorded in the subject's source documentation and, subsequently, on the appropriate AE reporting page of the subject's eCRF, whether or not they are considered causally related to study medication.

Regardless of causality, all SAEs must be recorded and reported from the time the patient signs the ICF at the Screening Visit until the final Follow-up Visit. Any SAE that occurs at any time after the specified follow-up period and which the Investigator considers study drug related should be reported immediately.

The initial SAE report should include the following information at minimum:

- Patient identification number
- Description and onset of the event
- Serious criteria
- Causality assessment to study drug

In the event that a pregnancy occurs in a patient, study drug must be stopped at once and study personnel must report the pregnancy within 24 hours from the time that site personnel first learn of the pregnancy using the pregnancy notification form provided for this study. Study personnel must also make every reasonable effort to follow the pregnancy until resolution and report the outcome using the pregnancy outcome form provided for this study. If the pregnancy is associated with an SAE (eg, if the mother is hospitalized), a separate SAE form must be submitted.

All SAE and pregnancy information should be emailed to Covance as shown below.

All SAE and Pregnancy Report Forms should be emailed or faxed to:

[REDACTED]

or

Fax#: [REDACTED]

If follow-up is obtained, or is requested by Covance, the additional information should be emailed on an SAE or Pregnancy Report Form to Covance, in a timely manner according to the procedures outlined above. Copies of discharge summaries, consultant reports, autopsy reports, and any other relevant documents may also be requested.

Appropriate remedial measures should be taken by the Investigator using his/her best medical judgment to treat the SAE. These measures and the subject's response to these measures should be recorded. All SAEs regardless of relationship to study drug will be followed by the Investigator until satisfactory resolution, until the Investigator deems the SAE to be chronic or stable, or until the subject is lost to follow-up. Clinical, laboratory, and diagnostic measures

should be employed by the Investigator as needed to adequately determine the etiology of the event.

The Investigator will be responsible for reporting all SAEs to the IRB. Ironwood will be responsible for reporting to the regulatory authorities.

3.8.10

11. **What is the primary purpose of the following statement?**

12. **What is the primary purpose of the following statement?**

13. **What is the primary purpose of the following statement?**

14. **What is the primary purpose of the following statement?**

15. **What is the primary purpose of the following statement?**

16. **What is the primary purpose of the following statement?**

17. **What is the primary purpose of the following statement?**

18. **What is the primary purpose of the following statement?**

19. **What is the primary purpose of the following statement?**

20. **What is the primary purpose of the following statement?**

3.8.11

Term	Percentage
GDP	100
Inflation	95
Interest rates	92
Central bank	88
Monetary policy	85
Quantitative easing	85
Inflation targeting	85
Interest rate hike	85

3.8.12 Pharmacokinetic Assessments

Blood samples for PK assessments will be collected according to the [Schedule of Events](#).

3.8.13

A horizontal bar chart consisting of four solid dark grey bars. The bars are positioned side-by-side, with the second bar being the longest, followed by the third, then the fourth, and finally the first bar which is the shortest. The bars are set against a white background.

3.9 STUDY ACTIVITIES

3.9.1 Screening Period (Day -45 to Day -1)

3.9.1.1 Screening Visit (Days -45 to -15)

- Obtain informed consent
- Record demographics and medical history
- Review inclusion and exclusion criteria
- Review prior and concomitant medications (all medicines taken during the 30 days before the Screening Visit)
- [REDACTED]
- Record weight and height
- Perform physical examination
- Perform 12-lead ECG (if QTcF exceeds eligibility criterion, conduct 2 more ECGs and use average of 3 values for determination of eligibility)
- Record respiratory rate and oral temperature
- Record seated BP (average of 3 measurements) and pulse
- Collect blood and urine samples for:
 - Serum chemistry, hematology (CBC), coagulation
 - Urinalysis (may be collected at any time during study visit)
 - Urine albumin and creatinine (may be collected at any time during study visit)
 - Urine pregnancy test, as applicable (must be confirmed negative) (may be collected at any time during study visit)
 - Hemoglobin A1c
 - Urine drug screen (may be collected at any time during study visit)
 - HBsAg, HCV, and HIV screen
- Conduct AE evaluation
- Issue supplies and instructions for first-void urine sampling

Note: Screening Visit assessments may take place over more than 1 day. Patients may be rescreened should they discontinue in the Screening Period due to visit window deviations or other administrative reasons. In addition, laboratory values, ECG values, or BPs that are outside

the range specified in the protocol may be repeated to confirm eligibility during the Screening Period at the Investigator's discretion after consultation with the Medical Monitor.

3.9.1.2 Baseline Visit (Days -7 ±3)

- Return by patient:
 - 2 first-void urine samples
- Review inclusion and exclusion criteria
- Review prior and current medications
- Record weight
- Perform 12-lead ECG (if QTcF exceeds eligibility criterion, conduct 2 more ECGs and use average of 3 values for determination of eligibility)
- Record seated BP (average of 3 measurements) and pulse
- Begin ABPM; patient will wear ≥24 hours and should return monitor to clinic at next study visit
- Collect blood and urine samples for:
 - Serum chemistry, hematology (CBC), coagulation
 - Urinalysis (may be collected at any time during study visit)
 - Urine pregnancy test, as applicable (must be confirmed negative; may be collected at any time during study visit)
 - Hemoglobin A1c
 - Fasting plasma glucose and insulin
- Conduct AE evaluation
- Issue supplies and instructions for first-void urine sampling

3.9.2 Treatment Period (Day 1 to Day 87 ±3)

3.9.2.1 Randomization Visit (Day 1)

- Return by patient:
 - 2 first-void urine samples
 - ABPM cuff and monitor (may be returned outside of study visit)

- Collect predose urine samples for:
 - Pregnancy test, as applicable (must be confirmed negative before randomization)
 - Urine cotinine
 - [REDACTED]
- Confirm inclusion and exclusion criteria
- Review prior and concomitant medications
- Record weight
- [REDACTED]
- Record respiratory rate and oral temperature predose (≤ 30 minutes)
- Record seated-to-standing (orthostatic) pulse and BP predose (≤ 30 minutes)
- Collect predose (≤ 30 minutes) blood samples for:
 - Serum creatinine and glucose
 - [REDACTED]
 - PK
 - [REDACTED]
 - [REDACTED]
- Randomize patient
- Dispense study drug
- MEMS introduction
- Administer study drug (morning dose)
- Record respiratory rate and oral temperature at 1 hour (± 15 minutes) postdose
- Record seated-to-standing (orthostatic) pulse and BP at 1, 2, 4, and 6 hours (± 15 m) postdose
- Collect blood samples for PK at 1, 3, and 6 hours (± 15 minutes) postdose
- Conduct AE evaluation
- Issue supplies and instructions for first-void urine sampling

3.9.2.2 Week 1 Visit (Day 8 ± 1)

- Return by patient:
 - 2 first-void urine samples

- Study drug (Patients will bring in study drug dispensed on Day 1. MEMS Caps will be read, and the subject will be administered the Day 8 [± 1] study drug dose in the clinic from the Day 1 bottles. The subject will continue to dose from the Day 1 bottles until returning for the Week 4 Visit.)
- Collect predose urine samples for pregnancy test, as applicable
- Record concomitant medications
- Record weight
- Record respiratory rate and oral temperature predose (≤ 30 minutes)
- Record seated-to-standing (orthostatic) pulse and BP predose (≤ 30 minutes)
- Collect predose (≤ 30 minutes) blood samples for:
 - Serum creatinine and glucose
 - Hemoglobin A1c
 - Fasting plasma glucose and insulin
 - [REDACTED]
 - PK
- Review MEMS cap data
- Administer study drug
- Record respiratory rate and oral temperature at 1 hour (± 15 minutes) postdose
- Record seated-to-standing (orthostatic) pulse and BP at 1, 2, 4 and 6 hours (± 15 minutes) postdose
- Collect blood samples for PK at 1, 3, and 6 hours (± 15 minutes) postdose
- [REDACTED]
- Conduct AE evaluation
- Issue supplies and instructions for first-void urine sampling

3.9.2.3 Week 4 Visit (Day 29 ± 3)

- Return by patient:
 - 2 first-void urine samples
 - Study drug
- Collect predose urine sample for pregnancy test, as applicable

- Record concomitant medications
- Record weight
- [REDACTED]
- Record seated-to-standing (orthostatic) pulse and BP predose (≤ 30 minutes)
- Begin ABPM; patient will wear ≥ 12 hours and should return monitor at next study visit
- Collect predose (≤ 30 minutes) blood samples for:
 - Serum chemistry, hematology (CBC), coagulation
 - Hemoglobin A1c
 - Fasting plasma glucose and insulin
 - PK
- Review MEMS cap data
- Dispense study drug
- Administer study drug
- Conduct AE evaluation
- Issue supplies and instructions for first-void urine sampling

3.9.2.4 Week 8 Visit (Day 57 ± 3)

- Return by patient:
 - 2 first-void urine samples
 - ABPM cuff and monitor (may be returned outside of study visit)
 - Study drug
- Collect predose urine samples for pregnancy test, as applicable
- Record concomitant medications
- Record weight
- [REDACTED]
- Record seated-to-standing (orthostatic) pulse and BP predose (≤ 30 minutes)
- Begin ABPM; patient will wear ≥ 12 hours and should return monitor to clinic at next study visit

- Collect predose (≤ 30 minutes) blood samples for:
 - Serum creatinine and glucose
 - Hemoglobin A1c
 - Fasting plasma glucose and insulin
 - PK
- Review MEMS cap data
- Dispense study drug
- Administer study drug
- Conduct AE evaluation
- Issue supplies and instructions for first-void urine sampling

3.9.2.5 End of Treatment Visit (Day 87 ± 3)

- Return by patient:
 - 2 first-void urine samples
 - ABPM cuff and monitor (may be returned outside of study visit)
 - Study drug
- Collect predose urine samples for:
 - Pregnancy test, as applicable
 - Urinalysis
 - [REDACTED]
- Record concomitant medications
- Record weight
- Perform physical examination
- [REDACTED]
- Record respiratory rate and oral temperature
- Perform 12-lead ECG
- Record seated-to-standing (orthostatic) pulse and BP predose (≤ 30 minutes) (seated measurement will be the average of 3 measurements)
- Begin ABPM; patient will wear ≥ 24 hours and should return monitor to clinic at next study visit

- Collect predose (\leq 30 minutes) blood samples for:
 - Serum chemistry, hematology (CBC), coagulation
 - Hemoglobin A1c
 - Fasting plasma glucose and insulin
 - [REDACTED]
 - PK
 - [REDACTED]
- Administer study drug
- Collect blood sample for PK at 3 hours (\pm 15 minutes) postdose
- Conduct AE evaluation
- Issue supplies and instructions for first-void urine sampling

3.9.3 Follow-up Period (Day 87 \pm 3 to Day 115 \pm 3)

3.9.3.1 Follow-up Visit (Day 115 \pm 3)

- Return by patient:
 - 2 first-void urine samples
 - ABPM cuff and monitor (may be returned outside of study visit)
- Record concomitant medications
- Record weight
- [REDACTED]
- Record respiratory rate and oral temperature
- Record seated-to-standing (orthostatic) pulse and BP
- Collect blood and urine samples for:
 - Urine pregnancy test, as applicable
 - Serum chemistry, hematology (CBC), coagulation
 - Hemoglobin A1c
 - Urinalysis
 - PK
 - [REDACTED]
- Conduct AE evaluation

4. STUDY ENDPOINTS

4.1 PRIMARY ENDPOINTS

4.1.1 Primary Safety

- Incidence of TEAEs and study drug-related TEAEs

4.1.2 Primary Efficacy

- Change from baseline in UACR over Weeks 8 and 12

4.2 EXPLORATORY ENDPOINTS

5. STATISTICAL METHODS

5.1 GENERAL CONSIDERATIONS

Descriptive statistics (n, mean or geometric mean, standard deviation, coefficient of variation, minimum, median, maximum, 25th and 75th percentiles) will be calculated to summarize continuous variables. Frequency and percentage of patients in each category will be calculated to summarize categorical variables. Additional details regarding the statistical methods will be provided in the Statistical Analysis Plan (SAP), to be finalized before unblinding of the study.

5.2 DETERMINATION OF SAMPLE SIZE

Using an estimate of standard deviation of 0.67, (29) a sample size of 40 patients per treatment group would provide approximately 80% power to detect a mean between-group difference of -0.376 units in change from baseline in log-transformed UACR over 12 weeks, with a one-sided significance level of 0.05 for at least 1 dose versus placebo comparison. This difference corresponds to a 31% between-group reduction of geometric mean change from baseline in UACR. Assuming a drop-out rate of 20%, approximately 150 patients will be randomly assigned in a 1:1:1 ratio (approximately 50 patients per treatment group) to 20 mg IW-1973, 40 mg IW-1973, or placebo.

5.3 ANALYSIS POPULATIONS

The following populations will be defined for this study:

- **Safety Population:** The Safety Population will consist of all randomized patients who receive at least 1 dose of study drug. Patients in this population will be summarized according to the treatment they actually received.
- **Intent-to-Treat (ITT) Population:** The ITT Population will consist of all randomized patients who receive at least 1 dose of study drug. Patients in this population will be evaluated according to the treatment group they were assigned to at Randomization.
- **PK Population:** The PK Population will consist of all randomized patients who receive at least 1 dose of study drug and have at least 1 postdose PK parameter assessment.
- **Per-Protocol (PP) Population:** The PP Population will consist of all ITT patients who did not have any major protocol deviations or dose reduction.

5.4 PATIENT DISPOSITION

The total number of screened patients and the number of patients who are screen failures will be tabulated. The number of patients who were randomized and the number and percentage of patients included in each population will be presented by treatment group. The number and percentage of patients who completed the study or discontinued early, as well as the reasons for discontinuation, will be presented by treatment group.

5.5 DEMOGRAPHICS AND BASELINE CHARACTERISTICS

Demographic parameters (eg, age, sex, race, ethnicity, weight, height, body mass index [BMI]) and other baseline characteristics will be summarized by treatment group for the Safety and ITT Populations.

The number and percentage of patients with abnormalities in medical and surgical histories in each system organ class (SOC) and preferred term (PT) will be summarized by treatment group for the Safety Population.

5.6 DRUG EXPOSURE AND COMPLIANCE

Exposure to study drug, calculated as the number of days from the first dose taken to the date of the last dose taken, inclusive, will be summarized by treatment group for the ITT Population. The total number of doses taken between each scheduled visit and overall for the entire study will be calculated for each subject. Compliance will be based on the number of doses expected to be taken. Percent compliance for study medication will be summarized by treatment group and overall for the ITT Population. Compliance rates will also be categorized as missing, <80%, ≥80% and ≤120%, and >120% and summarized by treatment group.

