3.5.1.4 Dosage

Table 2 summarizes the dosage and dosing regimen for each treatment arm by Treatment Period week.

Table 2. Dosage by Week

Dose	Week 1, BID Dosing	Weeks 2 through 12, QD Dosing
20 mg	one 10-mg IW-1973 Tablet, orally twice daily	two 10-mg IW-1973 Tablets, orally once daily
40 mg	one 20-mg IW-1973 Tablet, orally twice daily	two 20-mg IW-1973 Tablets, orally once daily
Placebo	one matching placebo tablet, orally twice daily	two matching placebo tablets, orally once daily

BID=twice daily; QD=once daily

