3.5.4.2 Dose Reduction

Per Investigator discretion, on a per-patient basis, dose may be reduced by half, ie, from 2 tablets daily to 1 tablet daily (in the morning). Each patient's dose may only be reduced once and may not be increased after reduction. Investigators should notify the Medical Monitor of all decisions to dose reduce on a per-patient basis.

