5.10 SAFETY ANALYSES

All safety parameters will be analyzed descriptively for the Safety Population.

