5.10.1 Adverse Events

Adverse events will be coded using the latest version of Medical Dictionary for Regulatory Activities (MedDRA) available at the start of the study. Treatment-emergent adverse events (TEAEs) are those AEs that started or worsened in severity after the administration of study drug. TEAEs will be summarized for each treatment group by SOC and PT; PT and severity, by SOC; PT and relationship to study drug; and by SOC, PT, and baseline eGFR. If a patient has more than 1 TEAE coded to the same preferred term, the patient will be counted only once for that preferred term by identifying those TEAEs with the highest severity and the closest relationship to study drug.

In addition, the incidence of AEs leading to premature discontinuation of study drug will be summarized by treatment group. Listings of pretreatment AEs, TEAEs, severe TEAEs, study drug-related AEs, SAEs, AEs leading to study discontinuation, and AEs leading to death (if any) will be provided.

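### The protocol permits one dose halving, but the adverse event action list, the adverse event summaries and the exposure measure make no place for it

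*Protocol*

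**What the plan says.** **Dose reduction.** Protocol section 3.5.4.2 (Dose Reduction) leaves it to the investigator whether the "dose may be reduced by half, ie, from 2 tablets daily to 1 tablet daily (in the morning". This may happen once per patient and may not be reversed. Table 2 in section 3.5.1.4 gives the 40 mg regimen from Week 2 as "two 20-mg IW-1973 Tablets, orally once daily", so a halved 40 mg patient takes 20 mg a day, the daily amount of the 20 mg arm.

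**Adverse event record.** Section 3.8.9.4 (Recording Adverse Events) asks for the actions taken with study medication and lists three: none, temporary interruption, discontinuation. The list is introduced as complete, not as examples. Dose reduction is not on it.

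**Adverse event summaries.** Section 5.10.1 tabulates all treatment-emergent events by system organ class and preferred term, severity, relationship and baseline eGFR. The only summary tied to action on study drug is that "the incidence of AEs leading to premature discontinuation of study drug will be summarized by treatment group".

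**Exposure and compliance.** Section 5.6 defines "Exposure to study drug, calculated as the number of days from the first dose taken to the date of the last dose taken, inclusive", and this "will be summarized by treatment group for the ITT Population". Doses taken are calculated per patient, and compliance is set against the doses expected. The section does not say whether the expected number changes after a reduction.

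**Grouping.** For the Safety Population, section 5.3 states: "Patients in this population will be summarized according to the treatment they actually received". It does not say which treatment that is for a patient who started on 40 mg and was halved to 20 mg a day. The same section removes dose-reduced patients from the Per-Protocol Population.

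**The concern.** Section 2 makes safety and tolerability a primary objective. Section 3.5.3 explains that 20 mg was chosen for comparison with 40 mg partly because it had a lower incidence of adverse events. Whether patients could stay on 40 mg is therefore one of the questions the trial is meant to answer.

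A patient can leave 40 mg in two ways: by stopping, or by halving. The protocol records and tabulates the first as an adverse event outcome. It allows the second without giving it a category in the adverse event record or a row in any stated summary. The exposure figure does not help, because days at half dose and days at full dose count alike. The tables described in the protocol could then show similar exposure and similar discontinuation in the two dose arms while some of the 40 mg arm was in fact taking 20 mg a day.

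**Working it through.** **1. Actions allowed against actions recorded**

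| Action on study drug | Permitted by | In the 3.8.9.4 action list | Summarized by action in 5.10.1 |
|---|---|---|---|
| None | – | yes | – |
| Temporary interruption | – | yes | no |
| Halving, once | 3.5.4.2 | **no** | **no** |
| Discontinuation | 3.4.2, 3.7.1 | yes | yes |

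Sections 3.5.4.2 and 3.8.9.4 do not agree. Reductions themselves must be known, because 5.3 uses them to define the Per-Protocol Population and 3.5.4.2 requires the Medical Monitor to be told. What has no stated place is the link from an adverse event to the reduction.

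**2. What the exposure measure shows for a halved patient**

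Inputs: nominal last treatment day D = 87 (section 3.1); 2 tablets a day before halving and 1 after (3.5.4.2); 20-mg tablets in the 40 mg arm (Table 2). Full dosing and a last dose on Day D are assumed. The protocol states no figure of its own on this point to reproduce.

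For a patient halved from day d:

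- exposure by 5.6 = D = 87 days, whatever d is
- tablets taken = 2(d − 1) + (D − d + 1)
- tablets scheduled = 2D = 174
- mean daily dose = 40 mg × taken / scheduled

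| Halved from | Exposure, days | Tablets taken | Share | Mean daily dose |
|---|---|---|---|---|
| never | 87 | 174 | 100% | 40.0 mg |
| Day 8 | 87 | 2×7 + 80 = 94 | 54% | 21.6 mg |
| Day 29 | 87 | 2×28 + 59 = 115 | 66% | 26.4 mg |
| Day 57 | 87 | 2×56 + 31 = 143 | 82% | 32.9 mg |

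With D = 84 or 90, the visit window, the shares move by about 1 percentage point. They need no assumed reduction rate.

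**3. Whether doses taken and compliance would reveal it**

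This depends on two points that 5.6 leaves open.

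- *A dose read as a dosing occasion.* An unreduced patient has 2×7 + 80 = 94 occasions. A patient halved from Day 8 also has 94. The count shows nothing.
- *A dose read as a tablet (3.5.5 uses pill counts), expected number reset after reduction.* The halved patient shows about 100%.
- *A dose read as a tablet, expected number not reset.* The share is (d + 86)/174. It first reaches 80% at d = 54, where 140/174 = 80.5%; at d = 53 it is 139/174 = 79.9%. Every halving before Day 54 then falls below 80%, which section 5.8 lists as a major protocol deviation, although 3.5.4.2 permits the reduction.

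**4. Group level**

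The protocol gives no expected reduction rate. As an illustration only, suppose 10% to 30% of the 40 mg arm is halved between Day 8 and Day 29. The mean daily dose in that arm is then:

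- 10% from Day 29: 0.9×40 + 0.1×26.4 = 38.6 mg
- 30% from Day 8: 0.7×40 + 0.3×21.6 = 34.5 mg

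That is a shortfall of about 3% to 14% against 40 mg, with reported mean exposure unchanged at 87 days.

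**The case against.** The other side has several good points.

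- **Events that lead to a reduction are still counted.** A reader might infer that only events stopping the drug are counted, and that a halved patient therefore looks free of tolerability problems. Section 5.10.1 does not support that: every treatment-emergent event enters the incidence, severity and relationship tables, and incidence is the primary safety endpoint in 4.1.1. Only the fact that the event led to a reduction is lost.
- **The two populations hold the same patients.** A reader might see a serious mismatch in reporting exposure for the Intent-to-Treat Population and events for the Safety Population. Both consist of randomized patients with at least one dose, and they can differ only where treatment received differs from assignment. That alone has little effect.
- **Exposure in days is correct as defined.** The protocol does not call it days at 40 mg. A reader who counts only full-dose days could, under the 10% to 30% assumption, get means from 0.9×87 + 0.1×28 = 81.1 down to 0.7×87 + 0.3×7 = 63.0 days, and so an overstatement of 7% to 38%. That treats half-dose days as no exposure and rests on rates with no source in the protocol.
- **Extra exposure tables belong in the analysis plan.** This is fair for mean daily dose and days by dose level: section 5.1 defers further detail, and such tables would not contradict 5.6. It does not dispose of the action list. An analysis plan cannot tabulate an action category that the adverse event record does not hold; at best it could guess the link from dates.
- **Section 3.8.9.4 does ask for all actions.** A site might note a reduction anyway. But the closed list after that request points the other way, and a category completed only by some sites is not a reliable basis for a summary.

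**Conclusion.** The point holds in a limited form. The protocol allows a single irreversible halving, leaves it out of the actions recorded for adverse events, summarizes by action only events leading to discontinuation, and measures exposure in calendar days alone. As written, it has no stated way of showing adverse events that forced a reduction, although tolerability is a primary objective.

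For a single patient the size is firm: 87 of 87 exposure days against 54% of scheduled tablets when halved from Day 8, or 66% when halved from Day 29, assuming otherwise complete dosing to Day 87. For the arm it is unknown, since no reduction rate is given and 3.5.4.2 does not require that a reduction follow an adverse event.

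A reader might go further and conclude that the tolerability comparison is biased in favour of 40 mg. The document does not establish that. Safety is descriptive, no exposure-adjusted event rate is planned, reduction is open to all arms, and 5.3 does not say whether a halved patient is summarized under 40 mg or 20 mg. The supported statement is that information needed for the comparison is not secured. This is a cheap improvement, not a threat to the trial's main conclusions.

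**What to change.** 1. Reconcile 3.5.4.2 with 3.8.9.4 by adding dose reduced to the action categories, in the protocol and on the adverse event page of the case report form. This should come first, because it affects what is collected.
2. In 5.10.1, tabulate by treatment group the number and percentage of patients with an adverse event leading to dose reduction, and with one leading to reduction or discontinuation combined.
3. In 5.6, add days at the full assigned dose, days at the reduced dose and mean daily dose. State whether expected doses reset after a permitted reduction, and whether a dose means a tablet or a dosing occasion.
4. In 5.3, state in which group a patient with a permitted reduction is summarized for safety.

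The cost is one extra case report form category, a few sentences and a few table rows. The link between event and reduction cannot be assumed to be recorded already, so the form change is part of the cost. Exposure to and tolerability of 40 mg may look slightly less favourable. No dose or rule for managing patients is altered.
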